1.1 Background

1.1.1 Study design

This is a randomized, controlled, evaluator-blinded, multi-center study to evaluate the effectiveness and safety of *Restylane® Kysse* for lip augmentation and correction of perioral rhytids.

Approximately 280 subjects will be randomized in a 2:1 ratio of treatment to control and treated. Approximately 187 subjects will be treated with *Restylane® Kysse* and 93 subjects will receive the control in the lips and perioral rhytids and will be followed for 48-weeks.

Investigator blinding will be accomplished by using a Treating Investigator to administer the treatments and a Blinded Evaluator, to whom randomization and treatment are concealed, to conduct the blinded assessments.

Safety assessments will be performed by non-blinded personnel. Eligible subjects randomized to receive treatment will be injected by the Treating Investigator at Day 1.

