[figure not shown]
	<small>Title</small> CTN 05DF1807 CIP Phase IV Study on Restylane Kysse, Canada	Doc id [REDACTED]
--	---	----------------------

Post Marketing study to evaluate lip enhancement, naturalness and partner/subject satisfaction after treatment with Restylane Kysse

Study products: Restylane® Kysse, Restylane® Defyne, and Restylane® Refyne

Clinical trial number (CTN): 05DF1807

Sponsor:

Confidentiality Statement

This study protocol contains confidential information belonging to Q-Med AB. Except as may be otherwise agreed to in writing, by accepting or reviewing these materials, you agree to hold such information in confidence and neither disclose it to any third parties (except where required by applicable law) nor use it for any other purpose than in relation to the clinical study described herein.

Investigators and Study Administrative Structure

Sponsor: Q-Med AB

Medical expert:

Global Head of Clinical Development:

Clinical Project Manager:

Statistician:

[figure not shown]

Further details on all participating investigators and the complete administrative structure of the study are found in the study files.

Synopsis

Safety Objectives and Endpoints:	
• To evaluate the safety of Restylane Kysse, Defyne, and Refyne by assessment of adverse events (AEs) by the Treating Investigator throughout the study period.
○ Incidence, intensity, duration and onset of AEs collected during the study period post treatment.
Clinical Study Duration:	The total duration of the study is expected to be 6 months (includes two months of enrollment).
Duration of Subject Participation:	Clinical study participation for each subject is approximately 18 weeks if optional touch-up treatment is performed and 14 weeks if no touch-up treatment is performed.
Inclusion criteria (applicable to subject only if not otherwise indicated):	
2. Signed and dated informed consent to participate in the study and use of facial images for marketing purpose.3. Adult women and men who have a steady relationship with a partner since 6 months and intend to undergo lip augmentation.
Exclusion criteria:	
1. Subjects presenting with known allergy to hyaluronic acid (HA) filler or amide local anesthetics.6. Subjects with a previous implant other than HA in or near the intended treatment site.

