3.1 Objectives and endpoints

3.1.1 Primary objective and endpoint

Aesthetic improvement (overall appearance) with Restylane Kysse compared to pre-treatment, assessed by the subject 8 weeks after last treatment, using the Global Aesthetic Improvement Scale (GAIS). The response rate is defined as a subject with a rating of at least “Improved”.

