4.1 General outline

This is an open-label, phase IV, post-marketing study to evaluate aesthetic improvement and partner/subject satisfaction after treatment with Restylane Kysse, alone and in combination with Restylane Defyne and Restylane Refyne.

Approximately 50 to 60 subjects at 4 sites in Canada will be treated. Twenty subjects will be treated with Restylane Kysse in the lips only (Group A) and 30 to 40 subjects will be treated with Restylane Kysse in the lips and Restylane Defyne and/or Restylane Refyne in the facial wrinkles and folds (Group B). All injections will be per the IFUs. Optional touch-up treatment at Week 4 is allowed for all products injected at initial treatment.

The treating investigator will determine if a subject is placed in Group A or B based on the optimal outcome for the subject.

[figure not shown]
Adult women and men who have a steady relationship with a partner for 6 months and intend to undergo lip augmentation will be asked to participate in the study. Eligible subjects will be injected by the Treating Investigator at Day 1. If optimal correction of the lips or surrounding facial wrinkles and folds (if treated) is not achieved at the first treatment or if the aesthetic appearance could be further improved, a touch-up will be offered after 4 weeks; this decision should be agreed upon by the Treating Investigator and the subject. Touch-up treatment will not be performed if the subject has a disease or condition described in the exclusion criteria, or an ongoing treatment-related AE that in the opinion of the Treating Investigator would be worsened by a touch-up treatment.

The subjects will be treated to achieve optimal correction. Optimal correction is defined as the best possible aesthetic outcome as agreed to by the Treating Investigator and the subject.

The maximum volume recommended for both initial and touch-up treatments combined is 2.5 mL for Restylane Kysse, 6.0 mL for Restylane Defyne and 4.0 mL for Restylane Refyne.

Subjects will be contacted by telephone 72 hours after initial treatment and optional touch-up treatment (as applicable) and will have in-clinic follow up visits at 4 weeks and 8 weeks after the last treatment.

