8.2.4 Reporting of adverse events

Adverse event reporting on each subject shall start at Visit 1 (Screening). The reporting shall continue during each follow-up visit (including telephone contacts and extra visits between planned visits) until the last scheduled visit in the study, Visit 6 (Follow-up at 8 weeks after last treatment).

All AEs, non-serious as well as serious, are to be reported as an AE in the eCRF.

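### On the visible text, the SAP supplied with protocol 05DF1807 describes a different study; the sponsor must confirm which statistical plan belongs to this one

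*SAP*

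**What the plan says.** SAP 1.1.1 (Study design) begins "This is a randomized, controlled, evaluator-blinded, multi-center study to evaluate the effectiveness and safety of" Restylane Kysse. SAP 1.1.1 and 1.1.2 give about 280 subjects, randomized 2:1 to Kysse or Juvéderm Volbella XC, stratified by Fitzpatrick skin type and followed for 48 weeks. SAP 1.2.1, 1.4.1, 2.1 and 2.4.3 set the primary analysis: non-inferiority on change from baseline as rated by a blinded evaluator, two co-primary endpoints, a margin of 0.5 units, with success required in both ITT and PP. SAP 2.4.2 imputes missing primary data by hot deck.

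Protocol 4.1 (General outline) says "This is an open-label, phase IV, post-marketing study to evaluate aesthetic improvement and partner/subject satisfaction after treatment with Restylane Kysse", alone or combined with Restylane Defyne and Refyne. On size it says "Approximately 50 to 60 subjects at 4 sites in Canada will be treated". On allocation: "The treating investigator will determine if a subject is placed in Group A or B based on the optimal outcome for the subject". Protocol 6.2 lists no reference product. The primary endpoint in Protocol 3.1.1 is aesthetic improvement "assessed by the subject 8 weeks after last treatment, using the Global Aesthetic Improvement Scale (GAIS"), with a responder defined as a subject rated Improved or better. Adverse event reporting in Protocol 8.2.4 runs "until the last scheduled visit in the study, Visit 6 (Follow-up at 8 weeks after last treatment"). The synopsis puts participation at "approximately 18 weeks if optional touch-up treatment is performed and 14 weeks if no touch-up treatment is performed". Protocol 10.6 presents observed cases only and rules out imputation.

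**The concern.** A SAP should carry out the protocol it accompanies. This one differs from the protocol on allocation, blinding, comparator, sample size, primary endpoint, type of hypothesis, length of follow-up, analysis sets and missing-data rule. These differences are not separate faults. They all follow from the two documents describing different studies.

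Two things are at stake. If the SAP was meant for 05DF1807, its primary efficacy analysis cannot be carried out and its imputation rule contradicts Protocol 10.6. If it was filed here by mistake, both plans may be sound, but a reader cannot check this study against the plan filed with it. In both cases the visible SAP gives no usable analysis of the protocol's primary endpoint.

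**Working it through.** **1. Do the sample counts hold within each document?** If one document had a counting slip, that might explain the gap.

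- SAP 1.1.2 and 2.7: 234 evaluable, about 15% lost. 234 / (1 − 0.15) = 275.3, rounded up to 276, close to the stated 280.
- SAP 2:1 split: 280 × 2/3 = 186.7 and 280 / 3 = 93.3, matching 187 and 93. 234 × 2/3 = 156 and 234 / 3 = 78, matching exactly.
- Protocol 4.1: Group A 20 plus Group B 30 to 40 gives 50 to 60, as stated.

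The counts hold in each document. The step from power and standard deviation to 234 cannot be tested, because those inputs are not visible.

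**2. How far apart are the sizes?** 280 / 60 = 4.7 and 280 / 50 = 5.6. Rounding, drop-out, or counting evaluable instead of enrolled subjects cannot bridge that.

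**3. Follow-up.** Protocol 4.1 says "Optional touch-up treatment at Week 4 is allowed for all products injected at initial treatment", and the last visit is 8 weeks after last treatment.

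- No touch-up: 0 + 8 = 8 weeks after first treatment.
- Touch-up at Week 4: 4 + 8 = 12 weeks.
- The 4-week gap agrees with the synopsis: 18 − 14 = 4.
- The SAP follows subjects for 48 weeks and, in 2.5.1, counts Week 48 retreatments.

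**4. Side by side.**

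| Item | SAP | Protocol |
|---|---|---|
| Allocation | Randomized 2:1 (1.1.2) | Chosen by treating investigator (4.1) |
| Blinding | Blinded evaluator (1.1.1) | Open-label (4.1; also 10.7) |
| Comparator | Juvéderm Volbella XC (1.1.2) | None (6.2) |
| Size | About 280 | 50 to 60 |
| Primary endpoint | Two blinded-evaluator change scores (1.4.1, 2.4.3) | Subject-rated GAIS response (3.1.1) |
| Missing primary data | Hot deck (2.4.2) | No imputation (10.6) |
| Sets named | Safety, ITT, PP (2.2) | FAS, PP (10.3, 10.8) |

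**5. What would happen if the SAP were applied to this study?**

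- ITT requires randomization (SAP 2.2). Nobody is randomized under Protocol 4.1, so ITT holds 0 of the 50 to 60 subjects.
- PP is a subset of ITT, so it also holds 0.
- The primary contrast is control minus Kysse (SAP 2.4.3). There are 0 control subjects here, against 93 planned in the SAP, so it cannot be computed.
- The safety set requires only treatment with an investigational product, so it would not be empty.

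**6. Other signs.** The visible SAP does not mention Defyne, Refyne, Groups A and B, or partners. SAP 1.5 says that Section 8 of its protocol covers product palpability and lip texture, symmetry, movement, function and sensation. The contents list of this protocol shows Section 8 as laboratory assessments, adverse events and device deficiencies only.

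**The case against.** The strongest reply is that this shows no statistical error in either plan. The SAP's opening part, where a trial number would most likely stand, was removed before review, and the visible remainder carries none. If the SAP belongs to another Kysse study, the only fault lies in the set of documents. The empty analysis sets are then hypothetical, since nothing shows that anyone meant to apply a randomized-trial SAP here. This stands, and it limits the point to a mismatch that must be resolved.

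The documents also overlap. Both place the primary assessment 8 weeks after the last treatment. SAP 1.2.2 lists aesthetic improvement and subject satisfaction as secondary objectives, SAP 1.3 names GAIS, and SAP 2.4.4 gives an interval method for responders. This is true, but it does not reconcile the designs. SAP 2.4.1 places secondary efficacy in ITT, which would be empty here.

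A reader might be tempted to infer more than the documents support:

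- That 05DF1807 was analysed with the wrong plan. Nothing visible shows this SAP was used on it.
- That the protocol lacks a primary analysis or a sample size rationale. Protocol 10.1, 10.2, 10.4 and 10.9 are redacted or have no visible text, so their content is unknown, not absent.
- That FAS is the primary efficacy set. Protocol 10.3 ties FAS only to demographics, baseline and subject characteristics, and 10.8 mentions PP only for excluding deviations. The set assigned to the primary endpoint cannot be read.
- That the contents entry for Protocol 4.4 (randomization and blinding) implies a randomized study. Its text is not visible, and the design stated in 4.1 is open-label with investigator-chosen groups.
- That each document is free of internal conflict. Only sample counts and visit timing were checked. The SAP, for instance, gives the diary period as the first 4 weeks in 1.2.3 but 30 days in 1.6 and 2.5.3.

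**Conclusion.** The point holds as a document mismatch that must be fixed. The conflicting statements are printed in full in both documents, so redaction does not explain them, and no visible text reconciles them. Planned size differs 4.7- to 5.6-fold. Follow-up is 48 weeks, against about 8 to 12 weeks from first treatment. As written, the SAP's ITT and PP sets would be empty for this study and its primary contrast could not be computed.

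Confidence is high that the two documents describe different studies. It does not extend to the cause: misfiling of either document remains possible. The conclusion assumes that Protocol 4.1 states the true design and that the removed and redacted parts do not contradict the printed text.

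**What to change.** The sponsor should confirm which statistical plan belongs to CTN 05DF1807 and replace the mismatched document. That is the SAP, or the protocol if that is the misfiled one.

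For the protocol as supplied, the plan must:

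- analyse the stated primary endpoint, a GAIS rating of at least Improved 8 weeks after last treatment;
- use observed cases, as Protocol 10.6 requires;
- use the analysis set that the protocol itself assigns, which is not visible here and should be checked in the unredacted text;
- leave out the randomization-based sets, the non-inferiority rule and the hot deck imputation.

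The cost is a document check and a replacement. Study conduct does not change.

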1.1.2 Number of subjects and randomization

Approximately 280 subjects will be randomized to treatment or to control in a 2:1 ratio (treatment: control) stratified by FST (I-III, IV or V-VI) to achieve a total sample size of 234 evaluable subjects (156 randomized to *Restylane® Kysse*, and 78 to *Juvéderm Volbella® XC*). Subjects in the FST=I-III stratum will be further stratified by study centers; subjects in the FST=IV, or FST=V-VI strata will not be further stratified by study centers due to the small sample size.

Before starting the study, a randomization list will be prepared under the supervision of a designated statistician. Randomization will be performed using an Interactive Response System by assigning each subject to *Restylane® Kysse* or the control according to the randomization list.

1.2 Study objectives

1.2.1 Primary efficacy objective

The primary objective of the study is to demonstrate non-inferiority of *Restylane® Kysse* versus a control in lip fullness augmentation by comparing change from baseline in the Blinded Evaluator assessment [REDACTED] at 8 weeks after last injection.

1.2.2 Secondary efficacy objectives

- To evaluate the effectiveness of *Restylane® Kysse* in lip fullness augmentation based on the Blinded Evaluator assessment of MLFS in the upper and lower lip [REDACTED]

- To evaluate the aesthetic improvement of the upper perioral rhytids and oral commissures after treatment with Restylane® Kysse, based on the Blinded Evaluator assessment [REDACTED]
- To evaluate the aesthetic improvement (overall appearance) after treatment *Restylane® Kysse* [REDACTED]
- Subjects' satisfaction after treatment with *Restylane® Kysse* [REDACTED]
- Lip fullness compared to baseline, [REDACTED]

1.2.3 Safety objectives

- To evaluate all AEs at all visits and pre-defined, expected, post-treatment events reported during the first 4 weeks after treatment as recorded in the subject diary.
- To evaluate the safety assessment at all visits, as assessed by a qualified staff member:

- [REDACTED]
- [REDACTED]
- [REDACTED]

1.2.4 Exploratory objectives

- [REDACTED]

1.4 Efficacy endpoints

1.4.1 Primary efficacy endpoint

The primary end point is change from baseline in the blinded evaluator assessment

1.4.2 Secondary efficacy endpoints

1.4.3 Exploratory efficacy endpoints

Exploratory efficacy endpoints include:

- (i) Change from baseline in the blinded evaluator assessment

separated by the following subgroups:

- Study site
- Fitzpatrick skin types (I-III, IV and V-VI)
- Race

1.5 Safety assessments

The methods for collecting safety data are described in Section 8 of the Clinical Study Protocol (CSP) and includes the following: assessment of adverse events (AEs) by direct question to subject and evaluation of subject, as well as pre-defined, expected, post-treatment events reported in the subject diaries; evaluation of product palpability, lip texture, symmetry, movement, function and sensation; laboratory assessments (urine pregnancy test only); and device deficiencies.

Each AE, serious as well as non-serious, shall be assessed by the Investigator for causal relationship with the study product and its use (the injection procedure) and for seriousness (Yes or No) of the event.

A two-point scale (Yes or No response) shall be used for the causality assessments. The Investigators shall be asked to indicate a response to each of the following questions in the eCRF:

- “Do you consider that there is a reasonable possibility that the event may have been caused by the study product?”, and
- “Do you consider that there is a reasonable possibility that the event may have been caused by the device injection procedure?”

If any of these questions is answered with a ‘Yes’, the AE will be considered related. Each AE will also be assessed for causal relationship and seriousness by the Sponsor, in order to fulfil regulatory requirements. In case of disagreement, the AE will be classified as “Related”.

1.6 Safety endpoints

Safety endpoints include:

- (i) Incidence, intensity, duration, and onset of related Adverse Events (AEs) collected during the whole study
- (ii) Incidence, intensity, and duration (defined as number of days with the event) of pre-defined, expected post-treatment events collected using a subject diary for 30 days after each treatment and for each treatment area
- (iii) The safety assessment at all visits, as assessed by a qualified staff member:
 - [REDACTED]
 - [REDACTED]
 - [REDACTED]

Exploratory safety endpoints include:

- (i) Incidence and intensity of related AEs, separated by the following subgroups:
 - Study site
 - Injection volume
 - Fitzpatrick skin types (I-III, IV and V-VI)

[REDACTED]

2 Statistical Methods

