3.1.4 Safety endpoints

- Incidence, intensity, duration and onset of AEs collected during the study period post treatment.

4. Design of the Study

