10.5 Safety analysis

AEs will be coded according to MedDRA and summarized by system organ class (SOC), preferred term (PT).

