2.5.2 Adverse events

AE terms will be coded using MedDRA dictionary. A treatment-emergent AE (TEAE) is defined as an AE with a start date and time on or after the first study product injection. If relationship to treatment is missing, the event will be conservatively summarized as being related to study product. If intensity is missing, a separate category of missing intensity will be included in the summary table, and no imputation of intensity will be performed. Through the data cleaning process, all attempts will be made to avoid missing values for relationship and intensity.

All AEs will be presented in a by-treatment and by-subject listing, detailing the verbatim term given by the investigator, the preferred term (PT), system organ class (SOC), onset date, end date, intensity, outcome, relationship to study product, relationship to study product injection procedure, action taken with study drug, other action taken, affected treatment area, seriousness and criteria for seriousness. Serious AEs will be presented in a separate listing.

Time to onset of an AE will be derived as the start date minus date of most recent treatment. If the start date is missing, it will be assumed that the AE started on the day of most recent treatment.

Duration of an AE will be derived as the stop date minus the start date + 1. If the start date is missing, it will be assumed that the AE started on the day of most recent treatment. Missing stop date will not be imputed and therefore no duration will be calculated in these cases. Instead, the number of AEs that were ongoing at the end of the study will be given.

An overall summary of AEs will be presented by treatment. The summary will include the total number of events, frequency counts and percentages of subjects with:

- Any TEAE

- Any AE related to product and/or injection procedure
- Unrelated TEAEs
- No TEAEs reported

Summaries of related AEs (including the total number of events, frequency counts and percentages of subjects) will be displayed by treatment and treatment occasion according to the following:

- All AEs by SOC and PT in descending order of frequency (the combined frequency of both treatments)
- All AEs by SOC, PT, and maximum intensity (mild, moderate, or severe)
- All AEs by SOC, PT, and action taken (none, medical treatment, non-pharmacological treatment, subject withdrawn)

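### The SAP sets out to evaluate all AEs, but its tables by AE type, intensity, onset and duration cover only AEs classed as related, and safety assessment is unblinded

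*SAP*

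**What the plan says.** The objective in SAP 1.2.3 carries no causality restriction: "To evaluate all AEs at all visits and pre-defined, expected, post-treatment events". Endpoint (i) in SAP 1.6 does: "Incidence, intensity, duration, and onset of related Adverse Events (AEs) collected during the whole study".

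SAP 2.5.2 introduces its detailed AE tables in the same restricted way: "Summaries of related AEs (including the total number of events, frequency counts and percentages of subjects) will be displayed by treatment and treatment occasion". The bullets under that sentence are worded differently, for example ("All AEs by SOC, PT, and maximum intensity (mild, moderate, or severe"). The onset and duration summaries that close 2.5.2 are again for related AEs, and so are the subgroup tables in 2.5.5.

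On who judges, SAP 1.1.1 states: "Safety assessments will be performed by non-blinded personnel". Under SAP 1.5 the Investigator answers yes or no on causality, once for the product and once for the injection procedure, and one yes makes the AE related. The Sponsor also assesses every AE, and a disagreement is resolved as related. Under 2.5.2 a missing relationship is treated as related.

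AEs regardless of cause appear in an overall table by treatment (any TEAE, related, unrelated, none) and in by-subject listings, with a separate listing of serious AEs.

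**The concern.** The SAP describes a randomized comparison. Relatedness is a judgement made after randomization, and the text has safety assessed by people who know the treatment. If only events that pass this judgement are tabulated by type, the arm comparison for each type mixes how often the event occurred with how readily it was attributed. Different attribution for the two products can create an apparent difference or mask a real one.

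The objective also goes unanswered at the level of event type. A reader of the planned tables would learn how many subjects in each arm had any TEAE. The incidence by arm of a given preferred term, regardless of cause, would not be shown.

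**Working it through.** **Scope of each planned output for AEs (SAP text)**

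| Output | Section | Population of events |
|---|---|---|
| Objective | 1.2.3 | all AEs |
| Endpoint (i) | 1.6 | related |
| SOC/PT; by maximum intensity; by action taken | 2.5.2 | related (lead-in), all (bullets) |
| Days to onset and duration by SOC/PT | 2.5.2, end | related |
| Subgroup tables | 2.5.5 | related |
| Overall counts by arm | 2.5.2 | any, related, unrelated, none; no split by type |
| Listings | 2.5.2 | all AEs; serious AEs separately |
| Diary symptoms, 30 days after each treatment | 1.6(ii), 2.5.3 | no relatedness filter |
| Normal/Abnormal assessments by visit | 2.5.4 | no relatedness filter |

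The third row is ambiguous as written. The lead-in, endpoint 1.6(i), the onset and duration sentence and 2.5.5 all point to related only.

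**How attribution enters the table**

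The SAP gives no figure on this point to reproduce, so every rate below is an assumption. Let *p* be the true incidence, equal in both arms, *a* the investigator's probability of calling the event related, and *s* the probability that an independent sponsor assessor does so. Because disagreement counts as related, an event leaves the table only if both say no:

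tabulated incidence = p × [1 − (1 − a)(1 − s)]

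Take p = 0.20, with a = 0.90 in one arm and 0.70 in the other.

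- Investigator alone (s = 0): 0.20 × 0.90 = 18%; 0.20 × 0.70 = 14%. Gap 4 points.
- Sponsor with s = 0.50: 0.20 × (1 − 0.10 × 0.50) = 19%; 0.20 × (1 − 0.30 × 0.50) = 17%. Gap 2 points.
- All-cause table: 20% in both arms. Gap 0, whatever *a* and *s* are.

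**Range.** The ratio of tabulated incidences does not depend on *p*. With control events called related 80% of the time:

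| Kysse events called related | Ratio (Kysse/control), s = 0 | Ratio, s = 0.50 |
|---|---|---|
| 80% | 1.000 | 1.000 |
| 70% | 0.875 | 0.944 |
| 60% | 0.750 | 0.889 |
| 50% | 0.625 | 0.833 |

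The disagreement rule shrinks the distortion but removes it only when attribution is equal in the two arms.

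**Scale against chance.** With the planned 187 and 93 treated subjects, and 18% in the larger arm, the standard error of the difference is √(0.18 × 0.82/187 + 0.14 × 0.86/93) ≈ 4.6 points. The 4-point distortion in the example is therefore smaller than one standard error for a single event type.

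**The case against.** Several things count against a strong reading, and most of them stand.

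- **Rules that favour related.** Either of two questions can make an event related, the Sponsor assesses independently of a missing or negative answer, and doubt is resolved as related. All of these move events into the tables. What remains is the event that both parties call unrelated; the SAP does not say whether the Sponsor's assessor is blinded.
- **Unfiltered tables exist.** A reader might infer that the related-AE tables are the only event-level safety comparison. They are not. Diary symptoms such as bruising, swelling, pain and lumps are tabulated by severity and number of days with no causality filter, and so are the Normal/Abnormal assessments. However, the diary covers 30 days after each treatment while follow-up runs 48 weeks, and 2.5.3 does not spell out presentation by arm.
- **All-cause data are kept.** Broad differential attribution would appear as an opposite imbalance in unrelated TEAEs, and every AE is listed. Overall counts can still miss an imbalance in one preferred term, and a listing leaves the reader to build the table.
- **Descriptive analysis.** No between-arm safety test or decision rule is stated, so the issue is what the tables show.

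A reader might also infer that the SAP departs from its protocol, because Protocol 3.1.4 has the endpoint "Incidence, intensity, duration and onset of AEs collected during the study period post treatment" without restriction to related events. The documents do not support that. Protocol 4.1 describes an open-label study of 50 to 60 subjects with groups chosen by the investigator, whereas SAP 1.1.1 describes a randomized, controlled study of about 280. The protocol is therefore not evidence about this SAP.

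**Conclusion.** The point holds as a mismatch inside the SAP: the objective is all AEs, while the endpoint and every breakdown of investigator-recorded AEs by type cover related AEs. Because safety assessment is unblinded, a difference in a specific AE type outside the diary and Normal/Abnormal tables would not be shown free of attribution.

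It would go too far to say that the safety comparison is biased. The documents give no attribution rates, so neither the size nor the direction of any bias can be known, and with equal attribution there is none. The 18% versus 14% and 19% versus 17% figures illustrate the mechanism. They rest on an assumed 20% incidence, assumed attribution of 90% and 70%, and, for the second pair, an independent sponsor assessor calling 50% related in both arms. The change is worth making because it is cheap and removes the dependence on attribution; no efficacy, alpha or sample-size result is affected.

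**What to change.** - In SAP 1.6(i), define the endpoint on all treatment-emergent AEs, in line with 1.2.3.
- In SAP 2.5.2, add tables for all TEAEs by SOC and PT, by maximum intensity, and for onset and duration, by treatment and treatment occasion.
- Keep the related-AE tables as a subset, and reword the bullets beneath their lead-in so that they say related AEs.

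The events are already due to be collected, coded and listed, so the cost is SAP wording and extra table runs. The downside is a longer output set and higher displayed AE frequencies.
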